Participants will be assigned to attention control training or the comparison stimuli computer task in a double-blind randomized control trial design. Both computerized dot probe tasks display two stimuli on a computer screen, one above the other, followed by a small right or left arrow appearing in the location vacated by one of the faces (see figure below). Participants are required to respond as quickly as they can by pressing the indicated right or left arrow on their computer keyboard without compromising accuracy.

In all trials, attention control training will present one neutral and one threatening stimulus on the screen. In most aspects of the study, the stimuli will be pictures of facial expressions. Specifically, in attention training, the participant will view one neutral face and one angry face on the screen at the same time. In the comparison condition, the

stimuli will always be two neutral faces presented before responding to the arrow.

Our investigational intervention = Attention Control Training will consist of:

- 6 sessions lasting approximately 10 minutes each.
- Each session will consist of 128 presentations of pairs of neutral and threatening stimuli, followed by the presentation of a response cue (right or left arrow to be clicked on a computer keyboard).
- Ideally participants will complete 2 sessions per week, allowing them to complete the trial in less than one month's time

Our comparison task will consist of:

- 6 sessions of a presumably inactive neutral-neutral intervention lasting approximately 10 minutes each.
- Each session will consist of 128 presentations of pairs of faces, followed by the presentation of a response cue (right or left arrow to be clicked on a computer keyboard).
- Ideally participants will complete 2 sessions per week, allowing them to complete the trial in less than one month's time.

IMPORTANTLY, after completing this inactive intervention and post assessment, all of these participants whose PTSD symptoms have not improved will be invited to return for a full trial of attention control training as described above to mitigate any concerns about a theoretically inactive intervention.

Aims for Clinical Trials

The major aims of the trials are straightforward:

- (1) Evaluate whether attention control training (ACT) is an effective therapy for reducing PTSD symptoms in combat veterans and/or women who have experienced interpersonal violence in comparison to a presumably inactive computer task.

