- (2) Evaluate whether ACT is an effective therapy for reducing associated symptoms of PTSD including anxiety, depression, emotion regulation difficulties, and substance use in comparison to a presumably inactive computer task in individuals with PTSD.
- (3) Compare the effectiveness of an online version of ACT delivered at a distance compared to in the clinic as well as a presumably inactive computer task for combat veterans with PTSD.

This study will be entered on ClinicalTrials.gov to formally register the project. We will add study number once approved by the registry.

Study Participants

Study 1: Recent combat veterans with symptoms of PTSD.

- We have a goal to recruit 100 veterans and active duty personnel serving in the U.S. Military since March 20, 2003 as potential participants for this aspect of the study.
- This sample will be randomly assigned to one of three study arms:
 - Attention control training at the clinic using faces as stimuli
 - Attention control training at the veteran's home via the internet using faces as stimuli
 - Comparison neutral-neutral task at the clinic using faces as stimuli
- Combat veterans with PTSD will be recruited from the community.
- Advertising on TV, with university veteran groups, with Lutheran Family Services, and from other groups serving veterans.

Study 2: Women exposed to interpersonal violence with symptoms of PTSD.

- Attention control training versus comparison task with a total of 60 women who have been exposed to interpersonal violence.
- We will use the faces version of the task with women.
- Participants will be randomly assigned to study condition.
- For safety, we will only include women who are not living with their abuser.
- We will ask about current safety before every session.
- Recruitment and sessions will occur at the Women's Center for Advancement (WCA) or at Creighton University if community women call to participate.

Measures

Demographics. All participants will answer standard demographic questions including age, gender, years of education, and marital status.

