- *Demographics*
- *Alcohol Use Disorders Identification Test*
- *Beck Anxiety Inventory*
- *Difficulties in Emotion Regulation Scale -16*
- *Drug Abuse Screening Test – 10*
- *Patient Health Questionnaire*

- *PTSD Checklist for DSM-5*
- *Threat-Related Attention Bias and Attention Bias Variability*

Participants who give consent and meet the study inclusion criteria but not exclusion criteria, will be randomly assigned to either attention control training or the comparison task in a double blind fashion. Those participants assigned to the neutral-neutral comparison condition will be given the opportunity to participate in ACT training immediately after completing session 8 if they are interested. They can participate in ACT in the clinic or from home online, so all participants will have an opportunity to receive the target intervention. If individuals participate in ACT after completing their participation in the neutral condition of the trial, we will ask them to complete the PCL-5 to assess PTSD symptoms at the end of their ACT training (either in the clinic or online through Qualtrics, Creighton University's online survey platform).

Sessions 2-7: Participants will complete short appointments for their computer attention training or comparison task session. Ideally participants will complete two training sessions per week, such that their participation from start to finish will complete in one month's time.

- For Study 1 sessions will occur in a private room at the Creighton University Psychology Department or online from the participants' personally selected private space (we are encouraging a quiet room in their home). For those participants completing training online, they will be asked to contact study investigators just before starting the task, to offer a relationship aspect to the online delivery and ensure they are conducting their training in a private setting.
- For Study 2 sessions will occur at the WCA or at Creighton University in a private room.

Session 8: Participants will return for a final appointment following training completion, and be reassessed with the same questionnaires and CAPS interview that were employed during the pretreatment assessment. (See the list below for post-intervention questionnaires.) The demographic, trauma screens, and M.I.N.I will be not readministered.

- *Clinician Administered PTSD Scale for DSM-5* (past week version)
- *Alcohol Use Disorders Identification Test*
- *Beck Anxiety Inventory*

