Important to consider when evaluating the risk/benefit ratio of this study, the VA/DoD (2010) Clinical Practice Guideline for the Management of Post-Traumatic Stress indicates that the mechanisms of action of current evidence-supported treatments for PTSD involve “repetitive review of traumatic memories and trauma-related situations” (p.43). Clearly the most unpleasant aspects of this project - thinking about their own traumatic experiences and related symptoms during the pre and post assessments are forms of exposure therapy. Such exposure is the active ingredient in our current most effective treatments for PTSD, and is considered standard practice in assessment and intervention for PTSD. We realize we are asking difficult questions, but those questions are being asked by or in the presence of our research staff with expertise and experience with PTSD in a private and comfortable setting. Although the assessments are potentially emotional, we also realize that talking about past traumas and symptoms is considered the gold standard of care for PTSD.

Nothing about the training sessions is expected to be difficult. The computerized attention training tasks are simple, brief, and easy. Those training sessions, and the intervention itself, are not associated with any known or expected risks to participants.

Potential Direct and Societal Benefits

If ACT is effective, participants' psychological symptoms may improve. We should note that ACT was shown to be effective in our previous studies, Badura-Brack, et al. (2015), and Khanna et al. (2015), so we are hopeful that this intervention will be effective again. Those participants who were randomly assigned to the comparison intervention will all be invited to continue on after completing formal participation in the study to complete the ACT training protocol in the clinic or online (whichever they prefer). Therefore all participants will have an opportunity to receive the active intervention within approximately 2 months time from initial study enrollment.

If ACT is shown to be effective, we are prepared to begin offering this very low cost,

easy to administer, and easy to experience intervention as therapy to people with PTSD in the near future. Additionally, if ACT is shown to effective at a distance over the internet, barriers to accessing psychological interventions for PTSD could be significantly reduced, because clients could log on to the website from home.

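### Session 8 follows the end of training and no outcome visit is described for those who stop, so online versus clinic (Aim 3) can be compared at different elapsed times and only among finishers

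*Combined protocol and SAP*

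**What the plan says.** Under Step by Step Procedures, the Session 8 paragraph sets the post-treatment visit by an event: "Participants will return for a final appointment following training completion". No day or week from randomisation, window, maximum duration or minimum number of sessions is given.

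The timing of training is a target: "Ideally participants will complete two training sessions per week, such that their participation from start to finish will complete in one month's time" (Sessions 2-7). The description of the intervention gives "6 sessions lasting approximately 10 minutes each" and the same ideal pace, "allowing them to complete the trial in less than one month's time". The comparison task has the same number of sessions and the same pace.

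Aim 3 is to "Compare the effectiveness of an online version of ACT delivered at a distance compared to in the clinic", and also against the inactive task. Study 1 has three arms. Two attend appointments on site; one trains in the participant's own private space after contacting staff.

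For people who stop early, the text covers only payment for sessions completed. Under Anticipated Risks, a referral for worsening or for suicidal or violent intent ends participation. Neither place mentions an outcome assessment. The 6-month and 1-year contacts collect the PCL-5 without the CAPS-5 and are counted from study completion. Proposed Analyses names methods but no analysis set, missing-data rule or adjustment for elapsed time.

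**The concern.** Followed as written, the plan produces Session 8 data only for people who finish six sessions, at a time that each participant's own pace decides. That matters most for Aim 3, because the randomised factor is how training is delivered, and delivery could plausibly affect both pace and finishing. If it does, two things other than the effect of delivery enter the online-minus-clinic estimate: symptom change that comes with time, and differences in who is left to be measured. Outcomes that were never collected cannot be recovered by adjustment. The later PCL-5 contacts do not repair this, since they lack the CAPS-5 and their starting point is undefined for someone who never finishes.

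**Working it through.** **Schedule, from the documents.** Duration = sessions / pace. At the ideal pace, 6 / 2 = 3 weeks, which agrees with the stated period of under a month. Nothing holds participants to it: 6 / 3 = 2 weeks, 6 / 1.5 = 4 weeks, 6 / 1 = 6 weeks.

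**Recall period.** The PCL-5 asks about the last month. If Session 8 comes directly after a training period of *d* days, the share of a 30-day recall month that precedes training is max(0, (30 − *d*)/30):
- 3 per week: (30 − 14)/30 = 53%
- 2 per week: (30 − 21)/30 = 30%
- 1.5 per week: (30 − 28)/30 = 7%
- 1 per week: 42 days exceeds 30, so 0%

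A difference in pace between arms could therefore move the PCL-5 with no difference in efficacy. The Session 8 CAPS-5 uses the past-week version, so this mechanism does not touch it.

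**Drift with time (all inputs assumed).** With a 2-week gap in mean interval, PCL-5 drift of 2 to 6 points per 4 weeks and SD 15: (2/4) × 2 to 6 = 1 to 3 points, and 1/15 to 3/15 = 0.07 to 0.20 SD. The sign depends on which arm is slower and which way symptoms drift.

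**Selection by finishing (all inputs assumed).** Take no true difference between modes. Let the baseline correlation be r = 0.6, so the residual SD is √(1 − 0.36) = 0.8. Let *u* be the standardised residual at Session 8 (higher = worse). The chance of finishing is logistic(*a* − *b·u*), with *a* set to give the arm's completion rate. Bias = 0.8 × [mean *u* among online finishers − mean *u* among clinic finishers]; a negative value favours online.

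| Completion clinic / online | *b* clinic / online | Bias (SD) |
|---|---|---|
| 83% / 68% | 0.5 / 0.5 | −0.06 |
| 83% / 68% | 1 / 1 | −0.10 |
| 83% / 68% | 0.5 / 1 | −0.15 |
| 83% / 68% | 0 / 1 | −0.22 |
| 68% / 83% | 0.5 / 0.5 | +0.06 |
| 68% / 83% | 1 / 1 | +0.10 |
| 68% / 83% | 0.5 / 1 | about 0 |
| 80% / 80% | 0.5 / 1 | −0.06 |
| 80% / 80% | 0 / 1 | −0.14 |

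Exchanging both the rates and the slopes between arms reverses every sign. If *b* is instead taken per SD of the full score, the values are somewhat smaller: 0.05 and 0.08 for equal slopes, and 0.05 and 0.12 in the last two rows.

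A normal selection model, ρ × [φ(z_on)/p_on − φ(z_cl)/p_cl] with ρ from 0.1 to 0.5, gives similar sizes: 0.02 to 0.08 SD at 90% v 80%, 0.03 to 0.15 at 90% v 70%, and 0.04 to 0.19 at 85% v 60%.

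**Scale.** The plan says "We have a goal to recruit 100 veterans and active duty personnel". No power calculation is given, so that number cannot be reproduced. Equal allocation (assumed) gives 100 / 3 ≈ 33 per arm. With 83% and 68% finishing, about 27 and 22 are observed, and the baseline-adjusted standard error is 0.8 × √(1/27.4 + 1/22.4) ≈ 0.228 SD. A bias of 0.09 SD then raises a two-sided 5% test to about 7%; a bias of 0.20 SD raises it to about 14%. For comparison, the unadjusted difference detectable with 80% power at 33 per arm is (1.96 + 0.84) × √(2/33) = 0.69 SD.

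**The case against.** All arms have the same six sessions, the same target pace and the same horizon of about a month. Assessing each person at the end of the course is a common pre/post design, and it answers a legitimate question: does ACT work equally well in either setting once delivered? Aim 3 speaks only of effectiveness and does not say that slow pace or stopping counts as part of it. A fixed date would catch some slow trainers mid-course, so the choice is partly one of estimand. Any artefact is also small beside the trial's own imprecision.

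Much of this stands, and it rules out several stronger readings.

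- A reader might infer that the arms *will* be assessed at unequal times. No pace by arm is given, so the text supports only *can*.
- A reader might infer a planned completers-only analysis. None is stated. The restriction comes from when Session 8 takes place, together with silence on the analysis set.
- A reader might take the remark that "barriers to accessing psychological interventions for PTSD could be significantly reduced" as a forecast that pace or completion will differ in the trial. It concerns future access to care if online ACT proves effective.
- A reader might conclude that the bias favours online. Swapping the assumed completion rates reverses the sign.

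What the objection does not answer is the person who stops training. For that person no Session 8 outcome is described, and an end-of-course rationale gives no reason to leave the outcome uncollected.

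**Conclusion.** The point holds as a design weakness. Session 8 is set by finishing, pace is only an ideal, and non-finishers have no described outcome visit. Aim 3 can therefore be compared at different elapsed times and only among finishers, without the protection of randomisation if delivery mode affects pace or finishing.

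The documents settle neither size nor direction. Under assumed completion of 83% and 68%, either way round, the selection bias is roughly 0.05 to 0.2 SD in either direction. The upper end needs outcome-related stopping to be stronger in one arm, which nothing in the documents shows. Equal completion alone does not guarantee zero: pace, completion and the link between outcome and completion must all be alike across arms. With finishers only, the effect on a 5% test is about 7% to 14% for biases of 0.09 to 0.20 SD. This is modest, but cheap to prevent, and it should be corrected.

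**What to change.** In the Session 8 paragraph:

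- Invite every randomised participant to Session 8, whatever number of training sessions was done.
- Set one common target time from randomisation, with the same window in all arms. The protocol's own month is the natural reference. Non-finishers are then assessed at that time.
- Leave the training schedule unchanged.
- Reconcile the new visit timing with the offer of ACT to comparison participants straight after Session 8, since a slow participant could reach that visit with the comparison task unfinished.
- State how an outcome visit fits with the referral text that ends participation.

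In Proposed Analyses: analyse everyone with data in the assigned arm, say how missing Session 8 data are handled, and record sessions completed and days from Session 1. Report pace and completion by arm as part of Aim 3. A completer analysis can be shown as supportive.

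Cost: protocol wording, plus a few extra Session 8 visits at the planned $50 each. Some slow trainers will be assessed before finishing. At one session per week, about four of six would be done by day 30 (30 / 7 ≈ 4.3).

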Difficulties in Emotion Regulation Scale -16 (DERS-16; Bjureberg et al., 2016). Comprised of 16 items, the DERS-16 provides a brief, yet comprehensive measure of emotion regulation abilities. The DERS-16 assesses five of the original six domains of emotion regulation including, for example, lack of emotional clarity, difficulty controlling impulsive behaviors when distressed, and limited access to emotion regulations strategies perceived as effective. Participants rate items such as "I have difficulty making sense out of my feelings" and "When I am upset, I become out of control" on a 5-point Likert scale (1=*almost never*; 5=*almost always*). The brief measure evidenced strong internal consistency, good test-retest reliability, as well as good convergent and discriminant validity in clinical and community samples. In addition, there were minimal differences in validity between the DERS-16 and the original, 36-item DERS (Bjureberg et al., 2016).

Drug Abuse Screening Test – 10 (DAST-10; Bohn, Babor, & Kranzler, 1991; Skinner, 1982). The DAST-10 is designed to provide a brief, self-report measure of substance abuse in the last 12 months. Specifically, participants are asked to consider their use of drugs such as cannabis, cocaine, hallucinogens, and narcotics, while excluding their use of alcohol and tobacco. Composed of 10-items, participants respond 'yes' or 'no' to questions such as "Have you ever experienced withdrawal symptoms (felt sick) when you stopped taking drugs?" and "Have you neglected your family because of your use of drugs?" DAST-10 scores range from 0 to 10 with higher scores indicative of more severe drug abuse. The DAST is a widely-used measure of substance abuse with sound psychometric properties. The DAST-10, specifically, has shown high internal consistency, adequate test-retest validity, and convergent and divergent validity with appropriate measures (Yudko, Lozhkina, & Fouts, 2007).

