- *Difficulties in Emotion Regulation Scale -16*
- *Drug Abuse Screening Test – 10*
- *Patient Health Questionnaire*
- *PTSD Checklist for DSM-5*
- *Threat-Related Attention Bias and Attention Bias Variability*

The participants will be paid \$50 for both session 1 and 8 and \$20 each session 2-7, for a total of \$220 for their time and inconvenience if they complete all aspects of the study. If participants withdraw from the study, they will be paid for all completed sessions.

Follow up: We will contact the participants by email and/or phone to conduct a follow-up assessment at 6 months and 1 year after study completion. The follow up contacts will ask basic questions about any perceived changes since participating in the study, and have participants complete the PCL-5 to assess PTSD symptoms. Participants can complete follow-up phone calls, or online questionnaires via Qualtrics, if they prefer.

Confidentiality

All interventions will be delivered via laptop computer and will use internet versions of the tasks. The website is run by Tel Aviv University and has been designed in compliance with international privacy and data safety procedures. Each participant will be assigned an individual login code word, and will not enter their name or any personal identifier into the intervention website. The primary investigator will keep a list of code words linked to individual participants in her locked Creighton University office and also stored electronically using Office365 storage through her Creighton University account. She will share access to these files only with approved study investigators who need contact information for the study.

All questionnaire data, including participant names, demographics, and questionnaire responses will be collected using Qualtrics, Creighton's online survey platform at Creighton University and this data is protected and data safety compliant. All study computers will be password-protected computers purchased through this study grant.

The only medical records used by this study are those data points collected directly for the purposes of this study.

Proposed Analyses

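### Names are collected in Qualtrics together with drug-use, alcohol, depression and PTSD answers, although each participant already has a code word; this is an avoidable re-identification risk that is cheap to remove

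*Combined protocol and SAP*

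**What the plan says.** The Confidentiality section describes two data systems and treats identity differently in each.

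- **Training website**, run by another university: "Each participant will be assigned an individual login code word, and will not enter their name or any personal identifier into the intervention website".
- **Link between code and person**: "The primary investigator will keep a list of code words linked to individual participants in her locked Creighton University office". A copy is kept electronically in Office365. On access: "She will share access to these files only with approved study investigators who need contact information for the study".
- **Questionnaires**, on the trial university's own survey platform: "All questionnaire data, including participant names, demographics, and questionnaire responses will be collected using Qualtrics". The protection offered is that "this data is protected and data safety compliant", together with password-protected study computers.

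The Step by Step Procedures list the AUDIT, BAI, DERS-16, DAST-10, PHQ-9 and PCL-5 at both Session 1 and Session 8. A further PCL-5 follows any crossover to active training, and others are due at 6 months and 1 year. These later ones may be completed through Qualtrics.

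**The concern.** The plan has a pseudonym for every participant but describes it only for the reaction-time and accuracy task. The more sensitive material, the questionnaire answers, is described as including names.

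The two populations make this more than a formality. For Study 1 the plan says "We have a goal to recruit 100 veterans and active duty personnel serving in the U.S. Military". On the DAST-10, "participants are asked to consider their use of drugs such as cannabis, cocaine, hallucinogens, and narcotics", and the instrument covers the preceding 12 months. For Study 2, the plan treats safety as a live issue: women must be living apart from the abuser, and safety is checked before each session. If the questionnaire data were misused or reached the wrong person, the answers would already be attached to a named service member or a named woman. The section on anticipated risks rates the project above minimal risk because of psychological discomfort and does not list loss of confidentiality.

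**Working it through.** The plan gives no figure on this point, so there is none to reproduce. The check sets the statements side by side and then counts what is held.

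**1. Identifiers.** On the training website, the participant is known by code word and enters no name. In Qualtrics, the plan's own sentence counts names as part of the questionnaire data. No code is mentioned for these records.

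**2. Separation.** For the website, separation is explicit: the code sits there and the link sits with the principal investigator. For the questionnaires, neither Confidentiality nor Proposed Analyses says that names are removed or stored apart before scoring or analysis.

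**3. Access.** The link list has an access rule (approved investigators who need contact information). The Qualtrics data have a general assurance and no stated access rule.

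**4. Amount held.** Item counts are from Measures and planned numbers from Study Participants.

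- Participants: 100 (Study 1 goal) + 60 (Study 2) = 160 at most.
- All self-report scales per session: AUDIT 10 + BAI 21 + DERS-16 16 + DAST-10 10 + PHQ-9 9 + PCL-5 20 = 86 items. Over Sessions 1 and 8: 2 × 86 = 172 per completer.
- The four instruments on drugs, alcohol, depression and PTSD: 10 + 10 + 9 + 20 = 49 items per session, or 2 × 49 = 98 per completer.
- Follow-up, if done online: 2 × 20 = 40 further PCL-5 items, plus 20 for anyone who crosses over.

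These counts describe the volume of identifiable data. They are not an estimate of the probability of disclosure, for which the documents give no basis.

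**The case against.** The strongest reply is that the two systems differ for good reason. The code word keeps names off a website run by another institution, whereas questionnaires stay on the trial university's own platform, which is said to be protected. On that view the plan is not inconsistent. It also names only the platform, and does not say that a name field appears on each DAST-10 or AUDIT form. The consent documents were not available for this review and may describe further protections.

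Much of this stands. It rules out calling the arrangement a contradiction, and it rules out saying that answers are exposed: no disclosure is described, and the link list as described holds codes and identities, not answers. What remains is that platform security does not separate names from answers, and the plan says that both are collected there.

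A reader might infer three stronger points, none of which the documents support.

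- *Named forms suppress honest reporting and bias the substance-use part of Aim 2.* Nothing in the plan addresses under-reporting. Staff ask the questions or are present, so a code would not make answers anonymous to them. Current substance dependence is an exclusion, which is a separate motive to deny use. Names are handled alike in every arm, so any such effect would not obviously favour one. Any attenuation figure would only restate an assumed rate of denial.
- *The code list gives staff a route to the allocation.* No statement says that a code word reveals or opens the assigned task to staff. That contact details sit in the same file is itself an inference from the access sentence.
- *Scorers may recognise participants.* The questionnaires are self-report and are summed, which leaves little room for a scorer's judgement.

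**Conclusion.** The point holds as a matter of participant protection. As written, sensitive answers are collected identifiably, with no described coding, separation or access rule, although a pseudonym already exists. In scale this concerns up to 160 people and 86 items at each of two sessions, with PCL-5 records possible for a year afterwards. The resulting risk is avoidable but cannot be quantified from the documents.

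The conclusion assumes that the Confidentiality section is the full description of how questionnaire data are handled. If the consent documents or a separate data-management procedure already provide coding, the point reduces to stating that in the protocol. It is a worthwhile low-cost improvement. It is not a threat to the validity of the comparison, and no effect on any estimate or on blinding has been shown.

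**What to change.** In the Confidentiality section:

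1. State that all Qualtrics questionnaires (Session 1, Session 8, after crossover, and at 6 months and 1 year) are completed under the existing code word or a study ID instead of the name.
2. Keep the name-to-code link in the principal investigator's restricted file.
3. Hold telephone and email details in a separate contact file.
4. State by role who may access each of the three: questionnaire data, link file and contact file.

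The cost is one changed field in the survey forms, one additional file and a few sentences of text. The small downside is that mistyped codes and remote follow-up records must be matched through the link file. Individual survey links would reduce typing errors, but sending them from within Qualtrics could put contact details back on the platform, so they should be sent from outside it. Re-identification for safety or follow-up remains possible through the link file.
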